### New Lesions

The appearance of new malignant lesions denotes disease progression; therefore, some comments on detection of new lesions are important. There are no specific criteria for the identification of new radiographic lesions; however, the finding of a new lesion should be unequivocal: i.e., not attributable to differences in scanning technique, change in imaging modality, or findings thought to represent something other than tumor (e.g., some 'new' bone lesions may be simply healing or flare of pre-existing lesions). This is particularly important when the participant's Baseline lesions show PR or CR. For example, necrosis of a liver lesion may be reported on a CT scan report as a 'new' cystic lesion, which it is not.

A lesion identified on a follow-up study in an anatomical location that was not scanned at Baseline is considered a new lesion and will indicate PD. An example of this is the participant who has visceral disease at Baseline and while on study has a brain CT or MRI ordered which reveals metastases. The participant's brain metastases are considered to be evidence of PD even if he/she did not have brain imaging at Baseline.

If a new lesion is equivocal, e.g., because of its small size, continued therapy and follow-up evaluation will clarify if it represents truly new disease. If repeat scans confirm there is definitely a new lesion, then progression should be declared using the date of the initial scan.

While fludeoxyglucose positron emission tomography (FDG-PET) response assessments need additional studies, it is sometimes reasonable to incorporate the use of FDG-PET scanning to complement CT scanning in assessment of progression (particularly possible 'new' disease). New lesions on the basis of FDG-PET imaging can be identified according to the following algorithm:

1. Negative FDG-PET at Baseline, with a positive FDG-PET at follow-up is a sign of PD based on a new lesion.
2. No FDG-PET at Baseline and a positive FDG-PET at follow-up: If the positive FDG-PET at follow-up corresponds to a new site of disease confirmed by CT, this is PD. If the positive FDG-PET at follow-up is not confirmed as a new site of disease on CT, additional follow-up CT scans are needed to determine if there is truly progression occurring at that site (if so, the date of PD will be the date of the initial abnormal FDG-PET scan). If the positive FDG-PET at follow-up corresponds to a pre-existing site of disease on CT that is not progressing on the basis of the anatomic images, this is not PD.

#### Evaluation of Best Overall Response

The best overall response (BOR) is the best response recorded from the start of the study intervention until the end of treatment taking into account any requirement for confirmation.

On occasion, a response may not be documented until after the end of therapy, so protocols should be clear if post treatment assessments are to be considered in determination of BOR. Protocols must specify how any new therapy introduced before progression will affect best response designation. The participant's BOR assignment will depend on the findings of both target and non-target disease and will also take into consideration the appearance of new lesions. Furthermore, depending on the nature of the study and the protocol requirements, it may also require confirmatory measurement. Specifically, in non-randomized studies where response is the primary endpoint, confirmation of PR or CR is needed to deem either 1 the 'BOR'.

The BOR is determined once all the data for the participant is known. Best response determination in studies where confirmation of CR or PR IS NOT required: Best response in these studies is defined as the best response across all time points (for example, a participant who has SD at first assessment, PR at second assessment, and PD on last assessment has a BOR of PR). When SD is believed to be best response, it must also meet the protocol-specified minimum time from Baseline. If the minimum time is not met when SD is otherwise the best time point response, the participant's best response depends on the subsequent assessments. For example, a participant who has SD at first assessment, PD at second and does not meet minimum duration for SD, will have a best response of PD. The same participant lost to follow-up after the first SD assessment would be considered inevaluable.

Target Lesions	Non-target Lesions	New Lesions	Overall Response
CRa	CR	No	CR
CR	Non-CR/non-PD	No	PR
CR	Not Evaluated	No	PR
PR	Non-PD or not all evaluated	No	PR
SD	Non-PD or not all evaluated	No	SD
Not all evaluated	Non-PD	No	NE
PD	Any	Yes or No	PD
Any	PD	Yes or No	PD
Any	Any	Yes	PD

a CR: complete response; NE: Not evaluable; PD: progressive disease; PR: partial response; SD: stable disease;. See text for more details.

**Note:**

When nodal disease is included in the sum of target lesions and the nodes decrease to 'normal' size (< 10 mm), they may still have a measurement reported on scans. This measurement should be recorded even though the nodes are normal in order not to overstate progression should it be based on increase in size of the nodes. As noted earlier, this means that participants with CR may not have a total sum of 'zero' on the eCRF.

In studies where confirmation of response is required, repeated 'NE' time point assessments may complicate best response determination. The analysis plan for the study must address how missing data/assessments will be addressed in determination of response and progression. For example, in most studies, it is reasonable to consider a participant with time point responses of PR-NE-PR as a confirmed response.

Participants with a global deterioration of health status requiring discontinuation of treatment without objective evidence of PD at that time should be reported as 'symptomatic deterioration'. Every effort should be made to document objective progression even after discontinuation of treatment. Symptomatic deterioration is not a descriptor of an objective response; it is a reason for stopping study therapy.

Conditions that define 'early progression, early death, and inevaluability' are study-specific and should be clearly described in each protocol (depending on treatment duration, and treatment periodicity).

In some circumstances it may be difficult to distinguish residual disease from normal tissue. When the evaluation of CR depends upon this determination, it is recommended that the residual lesion be investigated (fine needle aspirate/biopsy) before assigning a status of CR. The use of FDG-PET may be used to upgrade a response to a CR in a manner similar to a biopsy in cases where a residual radiographic abnormality is thought to represent fibrosis or scarring. The use of FDG-PET in this circumstance should be prospectively described in the protocol and supported by disease specific medical literature for the indication. However, it must be acknowledged that both approaches may lead to false positive CR due to limitations of FDG-PET and biopsy resolution/sensitivity.

For equivocal findings of progression (e.g., very small and uncertain new lesions; cystic changes or necrosis in existing lesions), treatment may continue until the next scheduled assessment. If at the next scheduled assessment, progression is confirmed, the date of progression should be the earlier date when progression was suspected.

## **CONFIRMATORY MEASUREMENT/DURATION OF RESPONSE**

### Confirmation

In non-randomized studies where response is the primary endpoint, confirmation of PR and CR is required to ensure the responses identified are not the result of measurement error. This will also permit appropriate interpretation of results in the context of historical data where response has traditionally required confirmation in such studies. However, in all other circumstances, i.e., in randomized studies (Phase II or III) or studies where SD or progression are the primary endpoints, confirmation of response is not required since it will not add value to the interpretation of the study results. However, elimination of the requirement for response confirmation may increase the importance of central review to protect against bias, in particular in studies which are not blinded.

In the case of SD, measurements must have met the SD criteria at least once after study entry at a minimum interval (in general not less than 6 to 8 weeks) that is defined in the study protocol.

### Duration of Overall Response

The duration of overall response is measured from the time measurement criteria are first met for CR/PR (whichever is first recorded) until the first date that recurrent or PD is objectively documented (taking as reference for PD the smallest measurements recorded on study).

The duration of overall CR is measured from the time measurement criteria are first met for CR until the first date that recurrent disease is objectively documented.

Duration of Stable Disease

Stable disease is measured from the start of the treatment (in randomized studies, from date of randomization) until the criteria for progression are met, taking as reference the smallest sum on study (if the Baseline sum is the smallest, this is the reference for calculation of PD).

The clinical relevance of the duration of SD varies in different studies and diseases. If the proportion of participants achieving SD for a minimum period of time is an endpoint of importance in a particular study, the protocol should specify the minimal time interval required between 2 measurements for determination of SD.

Note: The duration of response and SD as well as the progression-free survival are influenced by the frequency of follow-up after Baseline evaluation. It is not in the scope of this guideline to define a standard follow-up frequency. The frequency should take into account many parameters including disease types and stages, treatment periodicity, and standard practice. However, these limitations of the precision of the measured endpoint should be taken into account if comparisons between studies are to be made.

## Appendix 6 Clinical Laboratory Tests

Laboratory Assessments	Parameters			
Hematology	Platelet count	Mean corpuscular volume (MCV)	Mean corpuscular hemoglobin (MCH)	White Blood Cell Count with Differential: 
 
• Neutrophils
 
• Lymphocytes
 
• Monocytes
 
• Eosinophils
 
• Basophils
 

	Hemoglobin			
	Hematocrit			
Coagulation	Prothrombin time	Activated partial thromboplastin time	International normalized ratio	
Biochemistry	Blood Urea Nitrogen	Potassium	Aspartate aminotransferase	Total bilirubin
	Urea a	Creatinine	Sodium	Alanine aminotransferase
	Glucose	Calcium	Alkaline phosphatase	Protein
	Total amylase	Lipase	Gamma-glutamyl transpeptidase	Albumin
	Magnesium	Serum cystatin C (for sites where the test is available)	Phosphorus	
Details of liver chemistry stopping criteria and required actions and follow-up assessments after liver stopping or monitoring event are given in Section 7.1.				
Routine Urinalysis	
 
• Specific gravity, physical appearance, color
 
• pH, glucose, protein, blood, ketones, bilirubin, urobilinogen, nitrite, leukocyte esterase by dipstick
 
• Microscopic examination (if blood or protein is abnormal)
 
			
Other Screening Tests	
 
• Follicle-stimulating hormone (FSH) and estradiol (as needed if not a woman of child bearing potential only)
 
• Serum or highly sensitive urine human chorionic gonadotropin (hCG) pregnancy test (as needed for a woman of child bearing potential).
 
• Serology (HIV antibody, hepatitis B surface antigen [HBsAg], and hepatitis C virus antibody)
 
• All of the safety labs will be performed locally
 
			

a Urea can be calculated using blood urea nitrogen (BUN), as follows:

If BUN is expressed in mmol/L then urea=BUN (factor = 1 for conversions in mmol (1 mole N2 = 2 moles N per mole of urea) then urea [mmol/L] = BUN [mmol/L])

If BUN is expressed in mg/dL it needs to be converted according to the following formula: urea [mg/dL] = BUN [mg/dL] × 2.1428. (conversion factor derived by: MW of urea = 60, MW of urea nitrogen = 14 × 2 => 60/28 = 2.1428)

If BUN is expressed in mmol/L and needs to be converted to urea mg/dL, the following formula must be used: urea (mg/dL) = BUN (mmol/L) × 0.357.

**Appendix 7 Adverse Events: Definitions and Procedures for Recording, Evaluating, Follow-up, and Reporting****AE Definition**

AE Definition

• An AE is any untoward medical occurrence in a patient or clinical study participant, temporally associated with the use of study intervention, whether considered related to the study intervention or not.

• An AE can therefore be any unfavorable and unintended sign (including an abnormal laboratory finding), symptom, or disease (new or exacerbated) temporally associated with the use of study intervention. For surgical or diagnostic procedures, the condition/illness leading to such a procedure is considered as the AE rather than the procedure itself.

Events Meeting the AE Definition

• Any abnormal laboratory test results (hematology, clinical chemistry, or urinalysis) or other safety assessments (e.g., ECG, radiological scans, vital signs measurements), including those that worsen from Baseline, considered clinically significant in the medical and scientific judgment of the Investigator (i.e., not related to progression of underlying disease).

• Exacerbation of a chronic or intermittent pre-existing condition including either an increase in frequency and/or intensity of the condition.

• New conditions detected or diagnosed after study intervention administration even though it may have been present before the start of the study.

• Signs, symptoms, or the clinical sequelae of a suspected drug-drug interaction.

• Signs, symptoms, or the clinical sequelae of a suspected overdose of either study intervention or a concomitant medication.

• Lack of efficacy" or "failure of expected pharmacological action" per se will not be reported as an AE or a SAE. However, the signs, symptoms, and/or clinical sequelae resulting from lack of efficacy will be reported as an AE or a SAE if they fulfil the definition of an AE or SAE.

Events NOT Meeting the AE Definition


• Unless judged by the Investigator to be more severe than expected for the participant's condition, any clinically significant abnormal laboratory findings, other abnormal safety assessments that are associated with the underlying disease, the disease/disorder being studied, or expected progression, signs, or symptoms of the disease/disorder being studied.

• Medical or surgical procedure (e.g., endoscopy, appendectomy): the condition that leads to the procedure is the AE.

• Situations in which an untoward medical occurrence did not occur (social and/or convenience admission to a hospital).

• Anticipated day-to-day fluctuations of pre-existing disease(s) or condition(s) present or detected at the start of the study that do not worsen.

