#### Respiratory Disorders and ILD

Cases of ILD, which can be fatal, have been reported with the majority of patients from the Japanese population. Confounding or contributing factors, such as concomitant chemotherapy known to be associated with ILD, and pre-existing pulmonary diseases were frequent in fatal cases. Such patients should be closely monitored. In the event of symptoms (such as dyspnea, cough, fever) or radiographic findings suggestive of ILD, prompt diagnostic investigation should occur.

Patients with acute onset or worsening of pulmonary symptoms should be closely monitored. If interstitial lung disease is diagnosed, cetuximab must be discontinued and the patient be treated appropriately.

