#### *Cetuximab: Dose Modification*

In case a dose reduction is necessary, the study intervention will be administered as follows and described in the 'Investigator's Brochure Appendix' (part of the cetuximab IB, that refers to the Merck core company data sheet).

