**Recommended Dose Modifications for Tepotinib**

Target organ	Adverse event a	Dose modification
Pulmonary	Confirmed ILD/pneumonitis	Permanently discontinue tepotinib.
Cardiac	QTc interval prolongation of Grade $\geq 3$	Discontinue tepotinib
Body	Edema Grade 1 or 2	Dose level of tepotinib can be maintained
	Edema Grade 3	
The dose of tepotinib must be interrupted until edema recovers to <math>\leq</math> Grade 2 or baseline but for no more than 21 days.
 
After recovery the patient can restart at the same dose or at 250 mg daily.
 
If edema Grade 3 reoccurs the tepotinib dose must be interrupted again until edema recovers to <math>\leq</math> Grade 2 or baseline but for no more than 21 days. After recovery, tepotinib must then be dose reduced to 250 mg daily (if the previous dose was 500 mg daily).
 
If edema Grade 3 reoccurs at 250 mg dose, tepotinib must be permanently discontinued.

	Generalised edema Grade 4	Permanently discontinue tepotinib.
	Pancreatic enzyme elevation Grade $\geq 3$	See detailed instruction in Section 6.5.4.2.
Other	Any other related adverse event of Grade 3	
The dose of tepotinib must be interrupted until event resolves to <math>\leq</math> Grade 2 or baseline but for no more than 21 days. After recovery, tepotinib may be restarted at 1 dose level below; 250 mg daily.
 
If any other related AE of Grade 3 reoccurs at 250 mg dose, tepotinib must be permanently discontinued

	Grade 4	Permanently discontinue tepotinib

Abbreviation: AE = adverse event; .

Also consider DLT rules during DLT period and Safety Run-in.

a Adverse events graded by NCI-CTCAE v5.0.

Following dose modifications, the dose of tepotinib may be increased again to the initial dose level at the discretion of the Investigator.

Clinical circumstances which are not covered by above criteria may be grounds for dose reductions or treatment interruptions and should be discussed with the Sponsor on a case-by-case basis.

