### 6.6.3 Dose Limiting Toxicity

Dose-limiting toxicities will be evaluated using the NCI-CTCAE v5.0. Limits for dose escalations will be considered in accordance to Bayesian Optimal Interval design (BOIN) based on a maximum target toxicity rate of 30% and a maximum number of 12 participants (Yuan 2016).

In the safety run-in part of the study, DLTs are defined as any of the following toxicities and judged by the Investigator and/or the Sponsor to be not attributable to the disease or disease-related processes under investigation:

1. Grade 4 neutropenia for more than 7 days
2. Grade  $\geq 3$  febrile neutropenia with absolute neutrophil count  $< 1000/\text{mm}^3$  and a single temperature of  $> 38.3^\circ\text{C}$  ( $101^\circ\text{F}$ ) or a sustained temperature of  $\geq 38^\circ\text{C}$  ( $100.4^\circ\text{F}$ ) for more than 1 hour
3. Grade 4 thrombocytopenia or Grade 3 thrombocytopenia with non-traumatic bleeding
4. Grade 3 uncontrolled nausea/vomiting and/or diarrhea that has not improved within 72 hours despite adequate and optimal treatment
5. Grade 4 vomiting and/or diarrhea
6. Grade  $\geq 3$  skin toxicity that has not resolved to Grade 2 after 14 days of adequate treatment
7. Any other Grade  $\geq 3$  non-hematological AE will be defined as DLT. Exceptions are alopecia or an isolated lipase and/or amylase elevation of Grade  $\geq 3$  without clinical or radiological evidence of pancreatitis
8. Occurrence of Hy's law cases (defined as aminotransferases  $> 3 \times \text{ULN}$ , total bilirubin  $\geq 2 \times \text{ULN}$ , and alkaline phosphatase (ALP)  $< 2 \times \text{ULN}$ , with no other reason to account for these abnormalities)
9. Interstitial lung disease (ILD)/pneumonitis.

All participants enrolled in the safety run-in period who miss  $> 25\%$  of the planned doses of tepotinib and/or cetuximab within Cycle 1 will be replaced if the dose reduction/interruption was not caused by any safety reasons/DTLs. Participants who experience at least one DLT during the DLT assessment period are included regardless of the cumulative dose administered.

All participants enrolled in the study are selected based on the same inclusion and exclusion criteria as specified in the eligibility criteria.

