**Discontinuation of Study Intervention and Participant Discontinuation/Withdrawal**

## 7.1

**Discontinuation of Study Intervention**

In rare instances, it may be necessary for a participant to permanently discontinue (definitive discontinuation) study intervention. If study intervention is definitively discontinued, the participant will remain in the study to be evaluated for what is specified in the Schedule of Activities (SoA) (Section 1.3). The SoA indicates data to be collected at the time of discontinuation of study intervention and follow-up and for any further evaluations that need to be completed.

- The participant must be withdrawn from study intervention in the event of any of the following:
  - Withdrawal of consent.
  - Development of unacceptable toxicity.
  - Occurrence of progressive disease according to RECIST Version 1.1 or initiation of any other anticancer therapy.
  - Occurrence of an inclusion or exclusion criterion that is clinically relevant and affects the participant's safety, if discontinuation is considered necessary by the Investigator and / or Sponsor prior to study intervention completion.
  - Occurrence of pregnancy, which at the EoT visit is done as a serum test only for confirmation as urine test will be positive, before being discharged from the study.
  - Use of a nonpermitted concomitant drug (including any other drug with known anticancer activity unless specified otherwise), if discontinuation is considered necessary by the Investigator and/or the Sponsor.
  - Noncompliance that is deemed by the Investigator or the Sponsor to compromise participant safety or study integrity.

The Investigator will consider discontinuation of study intervention for abnormal liver function when a participant meets one of the conditions outlined and not meeting inclusion criterion 10 under Section 5.1 or if the Investigator believes that it is in best interest of the participant.

The Investigator must consider discontinuation of study intervention for an ILD-like event when a participant meets one of the conditions outlined in Section 6.5.4.1 and Section 6.5.4.2 under Respiratory Disorders and ILD, or if the Investigator believes that it is in best interest of the participant.

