If a clinically significant finding is identified (including changes from Baseline in QT interval corrected using Fridericia's formula [QTcF]) after enrollment, the Investigator or qualified designee will determine if the participant can continue in the study and if any change in participant management is needed. If the participant has a Grade  $\geq 3$  QTc interval prolongation study intervention must be discontinued. Additionally, close and appropriate ECG monitoring in hospital

according to local standard should be initiated. This review of the ECG printed at the time of collection will be documented. Any new clinically relevant finding is reported as an AE.

The SoA (Section 1.3) specifies the data to collect at study intervention discontinuation and follow-up, and any additional evaluations that need to be completed. Withdrawals will be documented in the eCRF as per the SoA (Section 1.3).

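### Appendix 6 sends the reader to Section 7.1 for liver stopping criteria and required actions, but 7.1 only asks the Investigator to consider stopping, and in no cycle does the protocol print a rule that stops both drugs for a Hy's law case

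*Protocol*

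**What the plan says.** Protocol Appendix 6, under the biochemistry panel, states: "Details of liver chemistry stopping criteria and required actions and follow-up assessments after liver stopping or monitoring event are given in Section 7.1".

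Section 7.1 has one sentence on the liver. It begins "The Investigator will consider discontinuation of study intervention for abnormal liver function when a participant meets one of the conditions outlined" and adds that the participant must also no longer satisfy inclusion criterion 10. The alternative trigger is the Investigator's view of the participant's best interest.

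Two other toxicities are handled differently:

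- **ILD.** The next sentence in 7.1 concerns "discontinuation of study intervention for an ILD-like event when a participant meets one of the conditions outlined in Section 6.5.4.1 and Section 6.5.4.2", so the reader knows where to look. Those sections hold firm stops. For cetuximab, 6.5.4.1 says "If interstitial lung disease is diagnosed, cetuximab must be discontinued and the patient be treated appropriately", and 6.5.4.2 permanently ends tepotinib once ILD is confirmed.
- **QTc.** For Grade 3 or higher, 7.1 says "QTc interval prolongation study intervention must be discontinued".

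Hy's law appears in the protocol as item 8 of the list in Section 6.6.3, which opens "In the safety run-in part of the study, DLTs are defined as any of the following toxicities". The SAP (Section 15.4) counts possible Hy's law cases over the on-treatment period, descriptively.

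**The concern.** A site that follows the Appendix 6 pointer expects thresholds, mandatory actions and a follow-up plan. It finds a request to consider stopping and a reference to conditions that are not there. No redaction in 7.1 explains the gap.

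The protocol itself treats the liver as a priority. Section 2.3 names AST/ALT increase beside ILD as an overlapping toxicity of the two drugs, and Section 8.3.7 makes drug-induced liver injury the only adverse event of special interest (AESI). Yet ILD and QTc prolongation carry mandatory stops, while the pattern most suggestive of serious liver injury does not. At stake is the safety of an individual participant, who could stay on cetuximab with that pattern without the site breaching any printed liver rule.

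**Working it through.** No arithmetic in the plan is at issue. The check is a cross-reading, plus one threshold comparison.

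**1. Does a Hy's law case trigger the 7.1 sentence?**

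- Definition (6.6.3 item 8): aminotransferases >3 x ULN, total bilirubin ≥2 x ULN, ALP <2 x ULN, no other explanation.
- Criterion 10 (5.1): total bilirubin ≤1.5 x ULN, with or without liver metastases. AST and ALT ≤3 x ULN, or ≤5 x ULN with liver metastases.
- Since 2 > 1.5, every Hy's law case fails criterion 10 on bilirubin alone.
- In 7.1, failing criterion 10 is joined by *and* to the unlisted conditions. That half of the trigger cannot be evaluated. Even if it is taken as met, the action is only to consider stopping.

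**2. Does any other printed rule require both drugs to stop?**

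| Place | What it requires in a Hy's law case | Liver-specific, mandatory and for both drugs? |
|---|---|---|
| 6.6.3 item 8 | Classifies it as a DLT in the run-in; this feeds the dose-level decision in 9.4.2.1 | No; orders no participant off either drug |
| 6.6.2 table, related Grade 3 | "The dose of tepotinib must be interrupted until event resolves to" Grade 2 or lower, or baseline, for at most 21 days; restart at 250 mg allowed | No; tepotinib only, no hepatic row |
| 6.6.2 table, Grade 4 | Permanent stop of tepotinib | No; tepotinib only |
| 6.6.1 | Infusion reactions and skin. Opens "In case a dose reduction is necessary, the study intervention will be administered as follows and described in the" appendix of the cetuximab IB, which is not among the documents | No liver rule printed |
| 6.5.4.1 | Among its organ-specific precautions, infusion reactions, ILD, skin, electrolytes and eye | No liver rule printed |
| 7.1, unacceptable toxicity | Withdrawal from study intervention | Mandatory and for both drugs, but undefined and not liver-specific |
| 7.1, eligibility criterion that arises on study and affects safety | Withdrawal if Investigator and/or Sponsor thinks it necessary | Discretionary |
| Section 8 | Immediate discussion with the Sponsor | No fixed outcome |
| 8.3.7, 8.3.3 and Appendix 7 | AESI report within 24 hours, follow-up, supplemental tests | No stopping action |

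No row meets all three conditions. Stopping tepotinib does not by itself end cetuximab: under 4.1, an adverse event ends the treatment period when it leads to discontinuation of both interventions. After a dose modification, 6.6.2 also lets the Investigator return tepotinib to its initial dose.

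**3. Does the SAP count the same cases?** Not exactly. SAP 15.4 uses ALT or AST ≥3 x ULN, bilirubin ≥2 x ULN and ALP ≤2 x ULN or missing, all on the same date, with no causality clause. Its enzyme cut-offs are slightly wider than those in 6.6.3, as suits a screen for possible cases.

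**The case against.** The strongest reply is that a real case would not go unmanaged. A related Grade 3 event interrupts tepotinib and a Grade 4 event ends it. Suspected drug-induced liver injury reaches the Sponsor within 24 hours. Section 8 calls for immediate discussion of continuation. The 7.1 bullet on eligibility criteria lets the Sponsor alone take a participant off both drugs, and if that bullet covers loss of an inclusion criterion, every Hy's law case qualifies through bilirubin. The cetuximab IB appendix may also contain a liver rule.

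Much of this stands. It makes prolonged dosing of both drugs unlikely, and it limits the cetuximab statement to what the protocol prints. It does not supply a mandatory liver rule for both drugs, and it does not mend the pointer.

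Three stronger readings are tempting and are not supported:

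- **That a Hy's law stop exists in the run-in and lapses afterwards.** Section 6.6.3 only classifies the event for the dose decision. The gap is the same in every cycle, so the share of participants treated outside the run-in does not measure it.
- **That a site may freely continue both drugs.** The tepotinib rows bind once the grade is reached. Whether a given case reaches Grade 3 depends on CTCAE cut-offs that the documents do not give, and the Grade 3 row also needs a judgement of relatedness.
- **That no liver rule for cetuximab exists anywhere.** The referenced IB appendix cannot be checked here.

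**Conclusion.** The concern holds in this form. Appendix 6 points to liver criteria, required actions and follow-up assessments that 7.1 does not contain. In no cycle, run-in or later, does the protocol print a liver-specific rule requiring both tepotinib and cetuximab to stop for a Hy's law case.

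It reaches every treated participant, at most 48 by plan. Its consequence cannot be sized further: no event rate is given, the number of cases may be zero, and the general safeguards would catch some or all of them. ORR and the other efficacy analyses are untouched. It is a participant-safety and clarity defect that should be corrected in the next amendment, not a threat to the trial's conclusions. The conclusion rests on the protocol text as printed and makes no claim about the unseen IB appendix.

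**What to change.** Rewrite the liver sentence in 7.1 in two parts:

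1. In any cycle, tepotinib and cetuximab must both be permanently discontinued for a case meeting the 6.6.3 item 8 definition: aminotransferases >3 x ULN, total bilirubin ≥2 x ULN, ALP <2 x ULN, and no other reason to account for it.
2. For other liver values outside criterion 10, the Investigator considers discontinuation. Delete the clause about unlisted conditions.

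Refer follow-up to 8.3.3 and Appendix 7, and change the Appendix 6 pointer to Sections 6.6.2 and 7.1. Extra repeat sampling could be added, but the correction does not depend on it.

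The cost is a text change. Investigators lose some discretion in Hy's law cases, but the requirement that nothing else explains the values keeps the causality judgement with them. That matters for participants with liver metastases, who may enter with AST/ALT up to 5 x ULN. The SAP need not change if its table is read as a screen on slightly wider enzyme criteria; the report should say that its counts need not equal the number of participants who met the stopping rule.
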